9.0 Privacy/Confidentiality Issues

Information produced by this study will be stored in the investigator's file and identified by a code number only. The code key connecting the patient's name to specific information about the patient will be kept in a separate, secure location. Information contained in the patient's records may not be given to anyone unaffiliated with the study in a form that could identify the patient without their written consent, except as required by law.

The results of this study may be published in a medical book or journal or used for teaching purposes. However, the patients' name or other identifying information will not be used in any publication or teaching materials without their specific permission.

The patient's name and social security number will be given to the business office for facilitating payment, but will not be used for any other purposes.

Leg thermotherapy for intermittent claudication

NCT02770547

Document Version: 12/11/2019

Statistical Analysis Plan

Demographic and clinical characteristics were summarized overall and by group. Two-sample tests, Wilcoxon Rank Sum test, Chi-square tests, or Fisher's Exact tests were used to compare the two groups. For the analysis of MRI-derived indices, absolute values were used for peak flow and flow per minute as sometimes the values reported from the machine were negative. Percentage change in peak flow is defined as $(\text{max absolute value} - \text{mean baseline absolute value}) / \text{mean baseline absolute value}$. For the outcome of 6-min walk test, the best of V1 and V2 was used as baseline. For the MRI-derived indices, the blood parameters, cutaneous microvascular function, and the experimental blood pressure, V2 was used as the baseline; while for the quality of life, V1 was used as the baseline. For physiological variables of systolic blood pressure, diastolic blood pressure, mean arterial pressure, heart rate, and temperature in the ear, change from baseline at each time point using the mean of total 18 sessions in two groups was plotted. Area under the curve (AUC), expressed as arbitrary units, for the total 90 minutes was plotted. The AUC for the change from baseline was also plotted in each session in each group. For the cutaneous microvascular function, mean arterial pressure, cutaneous vascular conductance (CVC) and MaxCVC were plotted by mean with standard error at each time point in each experimental visit; AUC for the total 14 time points were also plotted. In the experimental blood pressure, means with standard error were plotted for the change of systolic blood pressure, diastolic blood pressure and mean arterial pressure from baseline timepoint in high-heat therapy group or low-heat therapy group separately; change of AUC in systolic blood pressure, diastolic blood pressure and mean arterial pressure from baseline visit V2 were also plotted. For 6-min walk test, MRI-derived indices, blood parameters, quality of life, the AUC of cutaneous microvascular function indices, and AUC of experimental blood pressure, analyses were done with two different model types. First, linear mixed models with fixed effects for visiting time (V1 or V2, V3, V4) and intervention (high heat, low heat) were fit using the raw data. A significant interaction of time and intervention would indicate that there were differential effects of high and low heat over time. If the interaction was not significant, it was removed. In the main effects only model, a significant main effect for intervention would indicate that the two intervention groups are different (with the same magnitude of difference) across all time points (including baseline). Second, the changes from baseline to V3 and baseline to V4 were modeled with a linear mixed model. Here a significant interaction of time and intervention would mean the intervention effect was different at V3 vs V4. If the interaction was not significant, it was removed. In the main effects only model for change, a significant main effect for intervention would mean that there was an intervention effect, and it was of the same magnitude at V3 and V4. As the results were largely consistent, the results section focuses on the change score model results. Two sample t-tests were used to check whether the AUC for the change of physiological variables were different between two treatment groups. For the cutaneous microvascular function, the MaxCVC from two laser Doppler probes were compared at each timepoint using the linear mixed model with fixed effects for time point and probe, a significant interaction of timepoint and probe would indicate that the MaxCVC from two probes are different over time. The probe effects at each time point were also tested when the probe by time interaction was statistically significant at the significance level 0.05, or the main effects of probe were checked if the probe by time interaction was not statistically significant at the significance level 0.05. All analyses were performed using SAS v9.4.

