5.0 Study Procedures

After enrollment, subjects will be asked to complete two experimental sessions for baseline testing. The procedures involved in each visit, location and estimated duration are listed on Table 1. On **visit 1**, demographic and anthropometric characteristics from participants will be initially recorded. Subjects will then be asked about comorbid conditions, claudication history, and current medications and will fill out two questionnaires to assess generic (36-item Short-Form Health Survey) and disease-specific (Walking Impairment Questionnaire) quality of life. Next, subjects will be escorted to the examination room and will be asked to rest quietly for 15 min in the supine position. During this time, four NIRS (near infrared spectroscopy) sensors (Figure 2) will be attached to subjects’ two fingertips and two toes (left and right). These sensors are the same as the pulse oximeters used regularly in the hospital. We will monitor the blood flow during these 15 minutes while subjects are resting. After this rest period, systolic blood pressure will be measured in the arms (brachial artery) and ankles (posterior tibial and dorsalis pedis arteries) for the determination of the ankle brachial index. Subjects will then be familiarized with the 6-min walking test. A near-infrared spectroscopy (NIRS) system will be placed on the calf of the most symptomatic leg for monitoring leg oxygenation during the test. This exercise test consists of walking back and forth along a 100-ft corridor for 6 min. This session will be performed at the CTSI’s Clinical Research Center on the 5th floor of Goodman Hall and is expected to last approximately 2 hours.

Figure 2: Multichannel NIRS used to monitor the blood flow at two toes and two fingertips.

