Visit 2 will involve the assessment of the primary study outcomes, including vascular function and exercise tolerance. This session is expected to last approximately 4 hrs. Subjects will be asked to fast overnight prior to attending this session but will be permitted to take their usual morning medication regimen. The first exam will be the assessment of leg blood flow responses to circulatory occlusion (reactive hyperemia) using magnetic resonance imaging. This test will be performed at the Imaging Research Facilities in the basement of Goodman Hall. Next, subjects will be escorted to the CTSI's Clinical Research Center on the 5th floor. Subjects will initially be asked to lay supine and a nurse will place a catheter in one antecubital vein in the arm for venous blood sampling. After 10 min of rest, systolic blood pressures in the arms and in the ankles will be measured for the determination of the ankle-brachial index. Once the measurements are complete, a blood sample (20 ml) will be taken and the catheter will be removed. Next, subjects will be instrumented with laser Doppler probes placed inside local heaters for the assessment of cutaneous vascular reactivity. Two probes will be placed on the front portion of the most symptomatic leg and secured in place with tape. The sites where the probes are placed will be marked with a pen to allow for consistent placement in the second and third outcome measurement visits. The protocol consists of heating a site in the skin and measuring the changes in cutaneous red blood cell flux in response to the thermal challenge. Blood pressure and heart rate will be monitored during the test. This procedure will last approximately one hour. Next, the patients will perform the 6-min walking test. A near-infrared spectroscopy system, which measures skeletal muscle oxygenation, will be placed on the calf of the most symptomatic leg, secured in place with tape and covered with aluminum foil and a black Velcro strap. Similar to the laser Doppler probes, pen marks will be used identify the location of the probe. Subjects will be asked to walk back and forth along a 100-ft corridor for 6 min and report when the pain first appears. After the test is completed, subjects will be asked to grade the severity of the pain in the most symptomatic leg using the Borg-scale.

Visit #	Procedures	Location	Duration

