1	
 1) Medical History and Physical Examination 2) Quality of life assessment 3) Measurement of ankle-brachial index 4) Familiarization with the 6-min walking test 	CTSI's Clinical Research Center at Goodman Hall	2 hrs
2	
 1) Leg MRI (reactive hyperemia) 2) Catheter placement and venous blood draw 3) Measurement of ankle-brachial index 4) Assessment of cutaneous vascular function 5) 6-min walking test 	Imaging Research Facilities and CTSI's Clinical Research Center at Goodman Hall	4 hrs

Table 1: Procedures involved, location and estimated duration of visits 1 and 2.

After the baseline assessment is complete, subjects will be randomly allocated to one of two groups using a random allocation software. Participants will be asked to

attend **3 treatments sessions/week for 6 consecutive weeks**. These sessions will be conducted at the CTSI’s Clinical Research Center at Goodman Hall and will last approximately 110 min. A research coordinator will supervise the patients during the sessions. On each session, subjects will initially have their body weight and blood pressure measured and recorded. Next, patients will be asked to change into the water-circulating pants (Figure 3) and lay in semi-recumbent position. The garments will be connected to the water pump and the treatment will be applied for 90 min. In the high-heat group, hot water will be circulated through the garment with the goal of increasing skin temperature to 40°C, while thermoneutral water (33°C) will be used in the low-heat group. Subjects will be allowed to drink water ad libitum during the sessions but will not be allowed to consume food. At the end of the session, body weight and blood pressure will once again be recorded. The research coordinator will measure temperature (sublingual measurements) and blood pressure every 15 minutes during the treatment and will also inspect the skin in the legs to look for potential signs of injury or adverse reactions to the treatment. The subject will be asked to complete a heat sensation scale every 15 minutes during the treatment. The research coordinator will clean the garment after each use using a hospital-grade disinfectant spray. The garment will also be washed in a washing machine every week.

Figure 3: Water-circulating garment system for thermotherapy application

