Outcome measurements will be repeated after 9 sessions (3 weeks) and at the end of the treatment period (18 sessions). The protocol for these visits will be similar to visit 2, with the addition of quality of life assessment. The procedures involved are detailed on table 2. This visit is expected to last approximately 4.5 hrs. Subjects will be asked to fast overnight prior to attending this session but will be permitted to take their usual morning medication regimen.

Visit #	Procedures	Location	Duration
3 and 4	1) Leg MRI (reactive hyperemia) 2) Catheter placement and venous blood draw 3) Measurement of ankle-brachial index 4) Quality of life assessment 5) Assessment of cutaneous vascular function 6) 6-min walking test	Imaging Research Facilities and CTSI’s Clinical Research Center at Goodman Hall	4.5 hrs

Table 2: Procedures involved, location and estimated duration of visits 3 and 4.

Outcome Measures:

Reactive Hyperemia in the Popliteal Artery: Blood flow in the popliteal artery of the most symptomatic leg will be measured using MRI. We employed this technique in our initial study (IRB Protocol #1409063619). After the knee coil and the occlusion cuff are positioned on the most symptomatic leg, participants will be allowed to rest quietly for 15 min. Resting leg blood flow measurements and brachial systolic blood pressures will be completed every 5 min during this period. Next, a blood pressure cuff firmly wrapped around the lower thigh will be inflated to 75 mmHg above systolic blood pressure, or 250 mmHg, whichever is lower, for 5 min (8). Hyperemic flow will be measured for 10 min after cuff deflation. Flow reserve will be defined as the absolute difference between maximum hyperemic flow after cuff release and resting flow (9).

Cutaneous Microvascular Function: Laser-Doppler flowmetry probes, seated in the center of local skin heaters (Moor Instruments, UK), will be used to measure red blood cell flux, an index of skin blood flow (SkBF). Baseline SkBF will be recorded for 10 min after which local skin temperature will be increased to 39°C (0.1°C/s) and maintained at this level until a plateau is achieved (~40 min). Next, the local skin temperature will be elevated to 43°C, to induce maximal vasodilation. Cutaneous vascular conductance (CVC) will be calculated as laser-Doppler flux divided by mean arterial pressure (MAP), measured throughout the study via brachial artery oscillation, and normalized to maximal vasodilation (%CVC_{max}) (10, 11).

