8.0 Statistical Considerations

Sample size was estimated based on the ability to detect a significant change in 6-min walk distance from baseline to 6 weeks in the TT-treated group as compared to the control group. The studies of McDermott and co-workers (5) and Gardner and co-workers (2), which investigated the impact of home-based exercise training on walking tolerance in patients with IC, were used as a reference for the sample size calculations. We estimated the variance of improved walk distance by the MSE of Table 3 in the study of Gardner et al (2), which is 48.69 meters. Since both studies reported a non-significant change in 6-min walk in the attention-control group (95% confidence interval for McDermott's study is (-25.4 to 3.2) and for Gardner's study is (-6.33 to 14.33)), we predict that the change in 6-min walk in the control group, in our study, will be negligible (0). As pointed out by Perera et al (6), a change of 50 meters in the 6-min walk test is considered substantial and clinically meaningful in elderly subjects. Using this effect size $(50-0)/48.69$, we determined that **16 subjects per group** are needed to detect a substantial improvement by TT therapy with a power of 0.802.

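### Does taking the better of two pre-treatment walks as the 6-min walk baseline, against one walk at each follow-up, distort the trial's result?

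*SAP*

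**What the plan says.** **Baseline rule.** The SAP, which is a single section, says: "For the outcome of 6-min walk test, the best of V1 and V2 was used as baseline". Each other outcome whose baseline visit it names takes that baseline from one visit: V1 for quality of life, V2 for the rest.

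**The visits.** Protocol section 5.0 says of V1 that "Subjects will then be familiarized with the 6-min walking test", and Table 1 lists the item as "4) Familiarization with the 6-min walking test". Of V2 it says: "Visit 2 will involve the assessment of the primary study outcomes, including vascular function and exercise tolerance". For V3 (after 3 weeks) and V4 (at the end of treatment) it says: "The protocol for these visits will be similar to visit 2, with the addition of quality of life assessment". Table 2 lists one walk at each of these visits ("5) Assessment of cutaneous vascular function 6) 6-min walking test"). The SAP gives no best-of rule for them.

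**Randomisation.** Sections 4.0 and 5.0 of the protocol both place allocation after baseline testing is complete, and so after both walks.

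**Analysis.** The SAP fits a mixed model to the raw values and another to the changes from baseline, and says "the results section focuses on the change score model results". In both models the effects it interprets are the time-by-intervention interaction and, if that is dropped, the intervention main effect.

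**Sample size.** Protocol section 8.0 compares change at 6 weeks between the arms. It assumes 0 m in the control arm, 50 m in the treated arm and a spread of 48.69 m.

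**The concern.** The best of two noisy measurements is on average higher than either one alone. Here the baseline gets two attempts and each follow-up gets one, so the change score does not compare like with like. One of the two attempts is a walk that the protocol describes as familiarisation, and the SAP gives no reason for counting it.

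The effect is on the arm means of the change scores that the results section is to report, and on the time effect in the raw-data model. A stable control arm could appear to worsen. A treated arm that truly gains 50 m could appear to fall short of the change that the protocol calls clinically meaningful. A reader who sets arm means beside the 0 m and 50 m of section 8.0 could be misled. If the rule also reached the comparison between arms, the trial's main conclusion would be in doubt.

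**Working it through.** **1. The plan's own figure.** Inputs from protocol section 8.0 are a difference of 50 − 0 = 50 m, 48.69 m and 16 per group. The protocol calls 48.69 a variance (an MSE) but divides by it as an SD, and it is read as an SD here. Two-sided alpha of 0.05 is an assumption, because section 8.0 states neither alpha nor sidedness.

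- Noncentrality = (50/48.69) × √(16/2) = 2.90, with 30 degrees of freedom.
- Power from the noncentral t distribution = 0.8025, against 0.802 stated.

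So 0 m and 50 m enter the calculation only through their difference.

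**2. Shift within an arm.** Let g be the mean of V2 minus the mean of V1, and let s be the SD of a single walk around the patient's own level, with independent errors. Put t = √2 × s. Then

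shift = E[max(V1, V2)] − E[V2] = t·φ(g/t) − g·Φ(−g/t),

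which is s/√π when g = 0.

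The documents give neither s nor g. As an assumption, let 25%, 50% or 100% of the change variance 48.69² be walk-to-walk noise. Then s = √(share × 48.69²/2) = 17.2, 24.3 or 34.4 m. The 100% case is the ceiling if 48.69 m applies to this trial.

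| V1 mean relative to V2 | s = 17.2 m | s = 24.3 m | s = 34.4 m |
|---|---|---|---|
| 10 m longer | 15.5 | 19.3 | 24.8 |
| equal | 9.7 | 13.7 | 19.4 |
| 10 m shorter | 5.5 | 9.3 | 14.8 |
| 20 m shorter | 2.8 | 6.0 | 11.0 |
| 30 m shorter | 1.3 | 3.6 | 8.0 |

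The entries are metres by which mean change falls below change from V2. Each is also the practice gain from V2 to follow-up that would exactly offset the shift. In the middle case with equal means, a stable control arm would average −13.7 m and an arm that truly gains 50 m would average 50 − 13.7 = 36.3 m.

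**3. Comparison between arms.** Let B = max(V1, V2). Both walks precede allocation, so E[B] is the same in each arm. Hence

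E[V4 − B | high] − E[V4 − B | low] = E[V4 | high] − E[V4 | low].

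B drops out exactly, whatever s and g are. In the example above, 36.3 − (−13.7) = 50 m. The same argument holds for V3, for the V3/V4 main effect and for the interaction.

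**4. Simulation.** Settings: 16 per arm, 6,000 replicates per cell, assumed between-patient SD 80 or 100 m, the three values of s, g = 0 or 20 m, and no practice gain after V2.

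- Arm difference at a true 50 m: 49.6 to 50.7 m under every baseline rule.
- Type I error with best-of-two: 0.046 to 0.055.
- Power, V4 contrast: 0.81 to 0.87 with best-of-two; 0.80 to 0.82 with V2 alone; 0.80 to 0.89 with change from V2 and both walks as separate covariates.

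| SE of arm difference relative to best-of-two | V4 contrast | V3/V4 main effect |
|---|---|---|
| V2 alone | +1.3 to +9.0% | +1.6 to +13.3% |
| V2, with V1 and V2 as covariates | +2.6 to −4.3% | +2.2 to −9.0% |

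Best-of-two is more precise than V2 alone because it draws on both walks. For the V4 contrast, the covariate model gains clearly only when all the change variance is noise.

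**The case for a change.** The strongest case for a change is that the direction of the shift is certain. With any walk-to-walk noise, mean change from the better of two walks lies below mean change from V2. Only the 6-min walk, the outcome that sized the trial, is treated this way. The protocol supplies two arm-level figures that invite comparison. A test of change within an arm against zero would also go wrong: with no effect, no learning and 16 patients, it rejects about 37% of the time at a nominal 5%. Analysing change from V2, with both walks as covariates, needs no new data and costs at most about 3% in standard error in the simulation.

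The arithmetic stands, and so does the point about reading arm means. The case for changing the plan does not.

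- The SAP plans no within-arm test for this outcome and does not interpret the time main effect, so the 37% belongs to an analysis that is not in the plan.
- Section 8.0 uses 0 and 50 m as a difference, which the baseline rule leaves intact.
- V2 is not a clean reference either. It follows one earlier walk, while V3 and V4 follow at least two, so practice gain would remain in the within-arm change. The best-of-two shift acts against apparent improvement, not in its favour.
- Once V2 is a linear covariate, the V4 arm contrast is the same whether the outcome is change from V2 or V4 itself. Any gain in precision then comes from covariate adjustment, which is a separate matter.
- The SAP is written in the past tense and already describes its results as largely consistent. Moving the primary baseline now would be a choice made after the analysis.

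**Conclusion.** The plan can stand. The better-of-two baseline lowers mean change within each arm by an amount that the documents do not determine: 1.3 to 24.8 m over the assumed noise shares and V1-to-V2 gaps, before any practice gain after V2. It does not bias the difference between arms. That result needs only that both walks precede randomisation and that one rule serves both arms, and the documents establish both. Type I error stays at about 5%, and power for the V4 contrast is no lower than with V2 alone.

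The choice between best-of-two and V2 is a trade-off between two imperfect baselines. V2 alone loses precision, and V2 with two covariates has no reliable gain. A sensitivity analysis from V2, or a sentence warning against reading arm means beside 0 or 50 m, would be reasonable in a report, but neither would alter a planned result. Claims about the effect of heat should rest on the difference between arms, as the plan already has it.

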4.0 Enrollment/Randomization

Patients that fulfill the inclusion criteria and are interested in participating in the protocol will receive detailed instructions about the experimental set-up and

measurements and will be given a consent form. Once deemed eligible, patients will be asked to complete the baseline assessment. After the initial testing is complete, patients will be randomly allocated into one of two groups: low-heat therapy (control) and high-heat therapy. Medical devices and alternative therapies, such as massage and thermal-treatments have shown to be associated with high placebo responses (1). In order to control for this important psychological response, it is imperative to incorporate an appropriate placebo/sham intervention (1). In the present study, we will adopt strategies to minimize the potential confounding effect of psychological and perceptual responses to heat therapy. First, participants will be informed that the purpose of the study is to compare two ‘intensities’ of heat treatment. In the low-heat group, water at 33°C will be circulated through the garment during the treatment sessions. In our initial study (*IRB Protocol #1409063619*) we observed that this strategy evokes a small increase (~0.9°C) in leg skin temperature. In the high-heat group, hot water will be circulated through the garment during the treatment sessions with the goal of increasing skin temperature to 40°C, as observed in our initial study. A random allocation software (Research Randomizer, Social Psychology Network, <http://www.randomizer.org/>) will be used to perform the randomization.

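### In the SAP's raw-data model, dropping a non-significant visit-by-intervention term removes the treatment contrast and leaves a main effect that includes the pre-randomisation visit

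*SAP*

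**What the plan says.** The SAP analyses the 6-min walk test, MRI indices, blood parameters, quality of life and two sets of AUC outcomes with two model types.

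- **Raw-data model.** The first type is "linear mixed models with fixed effects for visiting time (V1 or V2, V3, V4) and intervention (high heat, low heat"). A significant interaction is taken to show that the two heat levels act differently over time. For a non-significant one the rule is: "If the interaction was not significant, it was removed". The main effect that remains is then read as meaning that "the two intervention groups are different (with the same magnitude of difference) across all time points (including baseline").
- **Change-score model.** The second type models the changes from baseline to V3 and to V4. With its own interaction removed, "a significant main effect for intervention would mean that there was an intervention effect, and it was of the same magnitude at V3 and V4".
- **Reporting.** The SAP states that the two sets of results mostly agreed, and on that ground "the results section focuses on the change score model results".

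Protocol section 4.0 fixes the timing of allocation: "After the initial testing is complete, patients will be randomly allocated into one of two groups". Protocol section 8.0 fixes the question: "Sample size was estimated based on the ability to detect a significant change in 6-min walk distance from baseline to 6 weeks" in the heat group compared with control.

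**The concern.** Because allocation follows baseline testing, the expected difference between arms at baseline is zero. A treatment effect in a model of raw values can therefore appear only as a group difference that changes after baseline, which is the visit-by-intervention term. The SAP's rule deletes that term when it misses significance. The main effect that replaces it pools a visit with no possible effect with two visits that may have one. It also carries the full between-patient variance and any chance imbalance that was present before treatment.

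Two things are at stake. A real effect that narrowly misses the interaction test is passed to a test of a different quantity with little power. And the SAP supports its choice of which results to feature by saying that the two models agreed. Where the interaction was dropped, that sets a treatment-effect estimate beside something that is not one.

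**Working it through.** **Inputs.** From Protocol section 8.0: 16 per group, a difference of 50 m, no change in controls, and 48.69 m, which the calculation uses as the SD of change. From the SAP: three visits in the raw-data model. Assumed, because the documents do not give them: two-sided alpha of 0.05 for these tests, compound symmetry (equal variances and one common correlation ρ), complete data, and ρ of 0.7 to 0.9.

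**1. The plan's own figure.** Noncentrality = 50 / (48.69 × √(2/16)) = 50 / 17.21 = 2.90 on 30 df. Power is 0.802, which matches the protocol.

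**2. What the raw-data main effect estimates.** Under compound symmetry each visit has weight 1/3.
- 50 m at V3 and V4: (0 + 50 + 50)/3 = 33.3 m.
- 25 m at V3 and 50 m at V4: (0 + 25 + 50)/3 = 25.0 m.

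**3. Power of that main effect.** Raw SD = 48.69/√(2(1−ρ)). The SD of a patient's three-visit mean is the raw SD × √((1+2ρ)/3). The standard error (SE) of the group difference is that SD × √(2/16).

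| ρ | Raw SD (m) | SD of mean (m) | SE (m) | Power, 50/50 | Power, 25/50 |
|---|---|---|---|---|---|
| 0.7 | 62.9 | 56.2 | 19.9 | 0.37 | 0.23 |
| 0.8 | 77.0 | 71.7 | 25.3 | 0.25 | 0.16 |
| 0.9 | 108.9 | 105.2 | 37.2 | 0.14 | 0.10 |

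**4. How often the fallback is reached.** The interaction F test has 2 and 60 df. Its noncentrality is the sum of squared deviations of the visit differences from their mean, divided by (48.69²/2) × (2/16) = 148.2.
- 50/50: 1666.7/148.2 = 11.25, power 0.84, so the term is dropped in about 16% of trials.
- 25/50: 1250/148.2 = 8.44, power 0.72, so it is dropped in about 28%.

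Under compound symmetry the two tests are nearly independent, so the powers in step 3 also apply within the trials that reach the fallback. For 50/50, the raw-data procedure as a whole misses the effect in about 0.158 × (1 − 0.37) = 10% to 0.158 × (1 − 0.14) = 14% of trials. For 25/50 it misses in 22% to 25%.

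**5. No true effect.** If either test were counted as evidence, the false-positive rate would be about 1 − 0.95² = 0.0975. Simulation gives about 0.10.

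**6. The change-score model on the same inputs.** The mean of the V3 and V4 changes has SD 48.69 × √0.75 = 42.2 m and SE 14.9 m. For 50/50 the expected main effect is 50 m with power 0.90. For 25/50 it is 37.5 m with power 0.68.

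**7. Sensitivity to the covariance structure.** The main effect is w′d, where d holds the three visit differences and w is S⁻¹1/(1′S⁻¹1) for covariance matrix S. Results for 50/50:
- AR(1) at 0.8 or 0.9, or Toeplitz at 0.85/0.75: baseline weight 0.43 to 0.48, estimate 26 to 29 m.
- Unstructured, relative SDs rising 1, 1.1, 1.2 (correlation 0.8): baseline weight 0.76, estimate 12 m.
- Unstructured, relative SDs falling 1, 0.9, 0.8 (correlation 0.8): baseline weight −0.11, estimate 55 m, so no shrinkage.

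If the effect wanes from 50 m at V3 to 25 m at V4, compound symmetry gives 25 m. That equals the V4 effect, although it is below the V3/V4 average of 37.5 m.

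**The case against.** The strongest reply is that this model does not carry the trial's conclusions. The change-score model is fitted to the same outcomes whatever the raw interaction test shows, it does not have baseline as an outcome, and the results focus on it. A reader might infer that the reported effect of heat is diluted by a third, or that the baseline-to-6-weeks question goes unanswered. The documents support neither reading.

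The SAP is also open about the raw-data term. It says that baseline is included and describes a difference between groups. It speaks of an intervention effect only for the change-score model, and in the raw-data model it ties treatment to the interaction. So a reader who concludes that the trial's type I error is 10% goes too far: that rate arises only if the baseline-inclusive main effect is taken as evidence of efficacy, which the SAP does not say.

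Nor is a shrinkage of a third or more a general result. It needs compound symmetry or something close to it, and an effect at V4 no smaller than at V3. The low power in step 3 applies only to the minority of trials that reach the fallback.

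All of this stands, and it limits the point. It does not make the fallback informative. The SAP still makes that term the reading of one of its two model types across every listed outcome group, and it uses agreement between the models to justify what it features. A null fallback result says little, and a positive one may reflect imbalance that predates treatment.

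**Conclusion.** The point holds within limits. Once the interaction is removed, the raw-data main effect pools a pre-randomisation visit with V3 and V4 and does not estimate the effect of heat. That follows from the model and the timing of randomisation, and needs no numerical assumption.

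Its size does need assumptions. With 16 per arm, an SD of change of 48.69 m, complete data and compound symmetry, 50 m becomes about 33 m and the 25/50 pattern about 25 m. Power for 50/50 is about 0.37 to 0.14 as ρ goes from 0.7 to 0.9, and the fallback is reached in about 16% (50/50) or 28% (25/50) of trials. The SAP states no covariance structure. Other structures give more shrinkage or none, and a waning effect can leave no shortfall against V4.

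The consequence is confined to the raw-data model and to the statement that the two models agreed. The featured change-score results are not diluted in this way. The change is worth making because it is cheap and would turn that statement into a real check.

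**What to change.** In the raw-data model:

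- Delete the step that removes a non-significant interaction, and the main-effect reading that includes baseline. Always keep visit by intervention.
- Constrain the two arms to a common baseline mean, or model V3 and V4 only with baseline as a covariate.
- State the covariance structure.
- Report the high-minus-low difference at V4, and at V3, with 95% CIs.
- Base the statement about agreement with the change-score model on those estimates.

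The cost is a short SAP edit and one re-run for each outcome group, on data already held. No new data are needed.
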